^c Approximately, the first 200 participants randomised will have a 24-week follow-up period post EOT: V18 (Week 58), V19 (Week 64), V20 (Week 70) and V21 (Week 76). If for any reason a participant in the first set of randomised participants as described, is not willing to participate for a full 24-week FU period and would like to terminate participation in the study, the follow-up discontinuation (FUD) visit should be performed at V19 (Week 64).

^d The remaining, approximately 200 participants randomised will have a 12 -week Follow-up period post EOT: V18 (Week 58) and V19 (Week 64).

^e Unscheduled visits may be initiated as needed, and additional assessments may be performed at these visits as indicated.

^f COVID-19 entry screening questionnaire must be completed for each participant prior to complete study visit activities. Sites should also follow local SARS-CoV-2 testing guidelines outside of CSP study assessments, if applicable.

^g UPSIT smell test will be performed in all countries participating in the study except in countries in which an UPSIT version is unavailable in the applicable native language.

^h The subjects, sites and sponsor will be unblinded to the FENO values prior to randomisation and blinded to the FeNO values post randomisation.

ⁱ Referral for CT scan should be provided at V2 (Week -2) and must be performed after nasal biopsy procedure (if applicable) at V2 only if the participant has met all eligibility criteria at V2. CT should be performed between V2 and V3 after the participant meets the inclusion/exclusion criteria and receive a confirmation from central readers that the inclusion criteria of NPS score is met.

^j The sponsor and site will be blinded to the immunoglobulin, eosinophil, basophil and monocyte counts from the central laboratory reports except screening visits (V1 and V2), any repeat testing that is performed during the screening period prior to Investigational Product (IP) administration at V3.

^k FSH test done only for female participants to confirm postmenopausal status in women < 50 years who have been amenorrhoeic for > 12 month.

^l At dosing visits, PK samples must be collected pre-dose.

- m Neutralising antibody (nAb) testing will be performed for all samples that are ADA positive. Samples that are ADA negative will not be tested for nAb.
- n For IPD, participants should only have nasal epithelial lining fluid collected if the time between randomisation and IPD Visit is \geq 24 weeks.

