should be checked by investigators during the study period. If a participant cannot tolerate MFNS or equivalent INCS during screening period, the participant should be screen failed.

The Principal Investigator should ask participants about SCS (oral and/or, parenteral) use for NP at each visit and record in the eCRF. Participants who require SCS and/or hospitalisation for an asthma exacerbation (see Section 8.2.5.2) or nasal polyp exacerbation during the screening period, should be screen failed and may rescreen once their symptoms improve (see Section 5.4.1).

Participants who experience an asthma exacerbation or worsening of nasal polyposis symptoms during the screening/run-in period (before Visit 2), may extend their screening period to accommodate the time needed for a short course (5-7 days) of systemic corticosteroids (SCS) treatment and return to Visit 2 no sooner than 4 weeks after the last dose of oral corticosteroids. If asthma exacerbation or worsening of nasal polyposis symptoms that require SCS or hospitalisation occurred between Visit 2 and Visit 3 (randomisation), participants should be screened failed and may be rescreened once their conditions are stabilised.

Participants will be provided with an electronic patient reported outcome (ePRO) device to record symptoms throughout the study (see Section 8.1.2). Participants who continue to meet eligibility criteria will be randomised 1:1 at Visit 3 (Day 0) to receive either placebo or tezepelumab 210 mg SC at randomisation (Week 0) and every 4 weeks thereafter (Weeks 4, 8, 12, 16, 20, 24, 28, 32, 36, 40, 44, 48). A total of 13 doses will be administered. An EOT Visit will be conducted at Week 52.

The first approximate 200 randomised participants will have a 24-week follow-up (FU) period without IP administration to assess durability of benefit. These participants will have the final safety assessment at Week 76. The remaining participants will be followed for 12 weeks after the end of treatment visit, with the final safety assessments at Week 64.

If for any reason a participant in the first set of randomised participants, as described above, is not willing to participate for a full 24-week FU period and would like to terminate participation in the study, the follow-up discontinuation (FUD) visit should be performed. The FUD visit should occur at V19 (Week 64).

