#### Additional FU Analysis Set

Additional FU analysis set comprises approximately the first 200 participants who have a 24-week follow-up period post EOT. Only participants who complete Week 64 visit are included in this analysis set, regardless of completion of Week 76 visit or withdrawal from the study after Week 64 visit.

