### 3.1.3 Study Periods

The following study periods are defined for analysis purposes:

- **Screening/run-in period:** starting on the date of the first study procedure and ending one day prior to randomisation (for randomised participants) or on the date of the last study procedure (for screening failures). If any participant is re-screened, the latest available screening will be used for this purpose.
- **Planned treatment period:** starting on the date of randomisation (efficacy) and ending on the date of the Week 52 visit or earlier study withdrawal date (for participants not followed up until Week 52). Unless noted otherwise, efficacy analyses will be based on planned treatment period.
- **On-treatment period:** starting on the date of first dose of IP and ending on the earlier (date of last dose of IP + 33 days, date of study withdrawal). Note: The 33 days is derived as dose frequency (28 days) plus 5 days as specified in the CSP Section 1.3.

- **Post-treatment period:** starting on the day after the end of the on-treatment period until the end of the study (Week 76 for the first ~200 participants and Week 64 for the remaining participants) or early withdrawal date.
- **On-study period** (planned treatment and follow-up): starting on the date of randomisation (efficacy) / date of first dose of IP (safety) and ending on the study completion or withdrawal date. For analyses performed at primary database lock, the on-study period is understood to include all data recorded up until the date of the data cut-off for the primary database lock (which includes all follow-up data available at the time of the data cut-off).
- **Additional FU period:** starting on the day after Week 64 visit until the end of the study (Week 76) or early withdrawal date. Only the first ~ 200 participants will continue follow-up beyond Week 64.

If a participant dies, the end dates of the study periods defined above will be capped at the date of death.

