### 3.6.2 General Adverse Events

Adverse events experienced by any participant at any time during the entire study will be coded using Medical Dictionary for Regulatory Activities (MedDRA V27.0). AEs will be categorised for analysis according to their onset date into the following study periods:

- AEs occurring during screening/run-in period: date of Visit 1 ≤ AE onset date < date of first dose of IP
- AEs occurring during on-treatment period: date of first dose of IP ≤ AE onset date ≤ earliest (date of last dose of IP + 33 days, date of death, date of study withdrawal)
- AEs occurring during post-treatment period: date of last dose of IP + 33 days < AE onset date ≤ study completion or withdrawal date
- AEs occurring during on-study period: date of first dose of IP ≤ AE onset date ≤ study completion or withdrawal date.
- AEs occurring during the additional FU period: date of Visit 19 ≤ AE onset date ≤ study completion or withdrawal date.

If the AE has a completely missing (and unresolvable) onset date, then the AE will be assumed to have occurred during the on-treatment period, unless the end date indicates unambiguously that the AE resolved before treatment started. If the AE has a partially missing (and unresolvable) onset date, then the AE will also be assumed to have occurred during the on-treatment period, unless either the end date indicates unambiguously that the AE resolved before treatment started, or the partial onset date is in the month/year prior to start of treatment.

The handling of partial/missing dates for AEs is detailed in [Appendix 8.3](#).

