In the above summaries, the exposure-adjusted incidence rate (EAIR) will be calculated for each treatment as the number of participants in that treatment group reporting the AE divided by the total time at risk in that treatment group, where time at risk is the time to the first event for a participant who experienced the event during the analysis period and time during the analysis period for a participant who didn't experience the event. EAIR will be reported as events per 100 participant-years. The 95CI% for EAIR difference will be calculated based on Miettinen and Nurminen's score method.

The overall AE categories summaries for on-treatment and on-study period will be repeated for the following subgroups:

- Age group (<65,  $\geq$ 65 years)
- Gender (Male, Female)
- Race (White, non-White)
- BMI (<25,  $\geq$ 25 to  $<$ 30,  $\geq$ 30 kg/m^2)
- Region (Asia Pacific including China and Japan, Europe, North America)

The EAIR (95% CIs) by subgroups for all AEs and SAEs will be presented on the forest plots.

Overall AEs as well as AEs and SAEs by SOC and PT summaries will be produced for the AEs with onset date during the additional follow-up period for the Additional FU analysis set.

The number and percentage of participant reporting COVID-19 AEs (as defined based on the COVID-19 MedDRA terms) is summarised by SOC and PT for the on-treatment and on-study periods. In addition, if there are more than 10 participants reporting COVID-19 AEs, then the AE listing is repeated including only these participants, with details of all AEs reported by these participants.

The adjudicated adverse events will also be summarised at subject level and event level for placebo-controlled on-treatment and placebo-controlled on-study period. In addition, the adjudicated MACE events, serious cardiac events, death, and malignancy will be presented by SOC, PT and causality (as determined by the IAC). The adverse events sent for adjudication will be listed together with the outcome of adjudication.

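### If participants leave at Week 64, the Week 64–76 adverse-event percentages are diluted; the SAP plans no exposure-adjusted rate for that period and gives it two start dates

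*SAP*

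**What the plan says.** **Who may leave.** For a participant in the first group of about 200 who does not want the full 24 weeks and "would like to terminate participation in the study, the follow-up discontinuation (FUD) visit should be performed at V19 (Week 64"), footnote c of the Schedule of Activities makes Week 64 the closing visit. Protocol 4.1 repeats it: "The FUD visit should occur at V19 (Week 64").

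**Who is in the set.** SAP 2.1.3 begins: "Additional FU analysis set comprises approximately the first 200 participants who have a 24-week follow-up period post EOT". It then gives the working rule: "Only participants who complete Week 64 visit are included in this analysis set, regardless of completion of Week 76 visit". By the same rule, nobody is taken out for leaving the study later on.

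**When the period starts.** SAP 3.1.3 defines the additional FU period as "starting on the day after Week 64 visit until the end of the study (Week 76) or early withdrawal date". SAP 3.6.2, which assigns events to periods, uses another start: "AEs occurring during the additional FU period: date of Visit 19 ≤ AE onset date ≤ study completion or withdrawal date".

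**What is tabulated.** SAP 4.2.10.1 plans overall, SOC/PT and SAE tables for this period: "summaries will be produced for the AEs with onset date during the additional follow-up period for the Additional FU analysis set". The statistic that section describes for such tables is the number and percentage of participants with at least one event. Exposure-adjusted incidence rates (EAIR) are listed for the on-treatment and on-study periods only.

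**The concern.** A participant whose last visit is Visit 19 meets the membership rule but has zero days in the period under 3.1.3, or one day under 3.6.2. That person adds one to the denominator and almost nothing to the chance of an event, so the percentage falls for reasons unrelated to safety. If the arms differ in how often people stop at Week 64, they are compared at different average time at risk.

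Protocol 4.2 gives off-treatment safety data as one purpose of the 24-week follow-up. These are also the only AE tables in SAP 4.2.10.1 confined to time off drug: the on-treatment tables stop at last dose plus 33 days, and the on-study tables pool everything from the first dose.

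Separately, an event dated on Visit 19 is inside or outside the period depending on which section the programmer follows.

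**Working it through.** The documents state no AE rate and no leaving rate for Weeks 64–76, so there is no planned figure to reproduce. The check is whether the definitions produce dilution, and how large it is under stated assumptions.

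**Inputs from the documents**
- Source group of about 200, allocated 1:1, so roughly 100 per arm (SAP 1.2, 2.1.3).
- Target days 449 (Week 64) and 533 (Week 76), SAP Table 1: 533 − 449 = 84 days for a participant who stays.
- Days at risk for a Week 64 leaver: 0 (SAP 3.1.3) or 1 (SAP 3.6.2).

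**Assumed inputs**
- f, the share of an arm's set that leaves at Visit 19: 0% to 30%.
- p, the 12-week AE risk among those followed: 10%, 20%, 30%.

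**Percentage as specified.** With N in the set, N(1 − f) are followed and N(1 − f)p have an event:

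reported % = N(1 − f)p / N = (1 − f)p

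| p (both arms) | f, tezepelumab / placebo | Reported, tezepelumab / placebo | Difference (points) |
|---|---|---|---|
| 20% | 0% / 0% | 20% / 20% | 0 |
| 20% | 10% / 10% | 18% / 18% | 0 |
| 20% | 20% / 20% | 16% / 16% | 0 |
| 20% | 10% / 20% | 18% / 16% | 2 |
| 20% | 10% / 30% | 18% / 14% | 4 |
| 10% | 10% / 30% | 9% / 7% | 2 |
| 30% | 10% / 30% | 27% / 21% | 6 |

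With equal leaving the ratio between arms is preserved, but both percentages and any difference shrink by (1 − f). Unequal leaving can also hide a difference: 20% versus 15% among those followed, with 30% versus 10% leaving, is reported as 0.7 × 20% = 14.0% versus 0.9 × 15% = 13.5%.

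**Percentage among those followed beyond Visit 19.** N(1 − f)p / N(1 − f) = p, so 20% versus 20% whatever f is.

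**EAIR with the SAP's own definition.** Time at risk is time to first event, or the whole period if there is none. Assume a constant hazard h over 84 days:
- h = −ln(1 − 0.20) / 84 = 0.22314 / 84 = 0.002656 per day.
- Mean time at risk per stayer = p / h = 0.20 / 0.002656 ≈ 75.3 days. A leaver contributes 0 days under the 3.1.3 start.
- EAIR = h × 365.25 × 100 = 97.0 per 100 participant-years in each arm, whatever f is.

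The same formula gives 45.8 at p = 10% and 155.1 at p = 30%, again free of f.

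**The case against.** **The set may already exclude Week 64 leavers.** Its first sentence speaks of people who have a 24-week follow-up, and its second tolerates withdrawal after the Week 64 visit, whereas these participants stop at that visit. The reading is possible, but nothing in the SAP excludes someone whose closing visit is Visit 19. The operative test is completion of Week 64 regardless of what follows, so a programmer would include them.

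**No leaving rate is given.** This stands. The protocol treats stopping at Week 64 as an exception, and if nobody uses it there is no dilution. A reader might infer that the tables will understate incidence; the documents support only that they would if people leave.

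**Events after Week 64 are analysed elsewhere.** This also stands. The on-study period runs to completion or withdrawal, and its tables and EAIR include these events. It would be wrong to say they are otherwise unreported. What is missing is an exposure-adjusted figure for this window alone, since on-study results pool it with the whole study.

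**Differential leaving will be visible.** SAP 4.2.1 reports follow-up completion and study discontinuation by arm. A reader can see the imbalance there, but the AE tables do not allow for it.

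**A motive for leaving.** A reader might infer that the Week 76 bar on biologics in Protocol 7.1.1 drives exits linked to disease control. That section is written for participants who stop IP early. Table 6 instead sets 4 months or 5 half-lives after the last dose, whichever is longer. Nothing ties leaving at Week 64 to either, so the point does not rest on this.

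**Crude percentages of everyone entering a period are common, and stayers are selected.** Both fair. These tables are descriptive with no test planned, and restricting to stayers does not yield an unbiased risk. Someone who stays one day past Visit 19 would still count in full. This is why EAIR is the more useful addition.

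**Conclusion.** The point holds as a conditional one. On the text, Week 64 leavers belong to the set with no time at risk in the period (at most one day), and the tables specific to that period carry no adjustment for time at risk. The reported percentage is (1 − f) times the percentage among those followed. At 20%, a leaving share of 10% to 30% gives 18% to 14%, and 10% versus 30% leaving creates a 4-point gap where those followed do not differ. Both the AE rates and the leaving shares are assumptions, and the actual size cannot be known from the documents.

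The mismatch between SAP 3.1.3 and 3.6.2 does not depend on any assumption, but it concerns a single day. Neither issue touches the efficacy analyses or the on-treatment and on-study safety results. This is a modest correction to descriptive tables, worth making because it is nearly free.

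**What to change.** In SAP 4.2.10.1:
- Add EAIR per 100 participant-years for the additional FU period, using the time-at-risk definition already in that section.
- Show, by arm, how many members of the set have follow-up beyond Visit 19, and use that number as the denominator for this period's AE percentages. State that these participants are a selected group and that the percentages are descriptive.

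In SAP 3.1.3 and 3.6.2, use one start date: the day after the Week 64 visit.

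Leave the set unchanged for the off-treatment efficacy analyses in SAP 4.2.9.1.

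The cost is a few lines of SAP text, one selection condition and one extra set of rates, with no new data. The denominator becomes slightly smaller. SAP 2.1.4 says the plan will not be updated after primary database lock, so the wording should change before then; otherwise the change would have to be described in the study report.

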#### **2.1.4 Handling of Other Issues Impacting Analysis Sets**

If it is found that any participant has been randomised on more than one occasion (contrary to the protocol) under different participant numbers, either at the same site or at different sites, then data corresponding to the first participant participation will be used in the analyses. Data associated with the second (and any subsequent) participation of the same participant will be listed and discussed in the CSR. All data associated with duplicate randomisations will be reviewed, and decisions regarding the analysis and reporting of these data will be documented, prior to unblinding at the primary database lock.

The above analysis set definitions assume the integrity of data captured from all participating sites in the trial. If it is deemed necessary to exclude participants from analysis sets due to suspected fraud/other serious non-compliance at a particular site, or to perform sensitivity analyses with participants from such a site removed for the same reason, the SAP will document this (amended if necessary) where possible prior to primary database lock. Otherwise, it will be fully described in the CSR. The SAP will not be updated after primary database lock.

In August 2023, the Japanese Ministry of Health, Labour and Welfare performed an inspection of an Site Management Organization (SMO) in Japan (Tokyo). This inspection identified significant deviations from GCP at the investigator sites supported by this SMO. Any Japanese participants enrolled from sites managed by the SMO (i.e. PPD [REDACTED] PPD [REDACTED] will be excluded from all analysis sets.

In May 2024, a critical data quality issue was identified at PPD [REDACTED] The NPSD data for the [REDACTED] randomized participants PPD [REDACTED] will be excluded from the analyses. Details will be described in the CSR.

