9.3 Populations for Analyses

The following populations are defined:

Table 14 Populations for Analysis

Population/Analysis set	Description
Enrolled	All participants who sign the informed consent form (ICF).
Randomly Assigned to Study Intervention	All participants randomised to study treatment (irrespective of whether treatment is subsequently taken).
Full Analysis Set	All participants randomised to study treatment who received at least one dose of IMP, irrespective of their protocol adherence and continued participation in the study.
Safety Set	All participants who received at least one dose of IMP.
Pharmacokinetic analysis set (PK)	All participants in the FAS who received active (tezepelumab) treatment and had at least one detectable tezepelumab serum concentration from a sample collected post-treatment that is assumed not to be affected by factors such as protocol deviations (PDs).

Efficacy analyses will be based on the FAS (defined above) according to their randomised treatment.

Safety analyses and anti-drug antibodies (ADA) analyses will be based on the safety analysis set, with participants assigned according to their actual treatment. Further details of how actual treatment will be determined for analysis in the event of treatment dispensing errors, etc. will be specified in the SAP. Any important deviations from the randomised treatment assignment, and any participants that have received investigational product without being randomised, will be listed and considered when interpreting the safety data.

All PK summaries will be based on the PK analysis set.

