#### Randomised Analysis Set

This analysis set comprises all participants randomised to study treatment, irrespective of whether IP was subsequently taken, and will also be used for the reporting of disposition.

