#### **2.1.2 Safety Set (SS)**

This analysis set comprises all participants who received at least one dose of IP.

Safety analyses will be performed using all participants in the safety analysis set. Participants will be analysed according to their actual treatment in the case of any discrepancies between randomised and actual treatment. Specifically, a participant who has on one or more occasion actually received active (tezepelumab) treatment will be assigned to the tezepelumab group, regardless of the randomised treatment assignment. A participant who has on no occasion actually received any active (tezepelumab) treatment will be assigned to the placebo group, regardless of the randomised treatment assignment.

Safety data will also be listed separately and discussed in the clinical study report (CSR) for any participant who received a treatment that was not the randomised treatment at one or more visits.

Summaries of ADA will also be based on the safety analysis set, using the same approach to handle treatment dispensing errors.

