## 2.2 Protocol Deviations

Only important protocol deviations (PDs) will be listed and tabulated in the CSR, and only for randomised participants (not screening failures). These are defined as PDs which may significantly affect the completeness, accuracy and/or reliability of the study data, or which may significantly affect a participant's rights, safety, or well-being. Important PDs in this trial will be grouped under one of the following categories:

- Did not fulfill key eligibility criteria
- Discontinuation criteria for study product met, but participant not withdrawn from study treatment
- Discontinuation criteria for overall study withdrawal met but patient not withdrawn from study
- Investigational product (IP) deviation
- Excluded medications taken
- Deviations related to study procedure
- Other important deviations

Important protocol deviations associated with the global/county situation will also be summarised separately (see Section 4.2.13).

Important PDs will be identified and documented by the study team prior to unblinding of the trial at the primary database lock. As far as possible, the occurrence of important PDs will be monitored (blinded) during the trial, with the emphasis on their future prevention.

With the exception of the PK analyses, important PDs will not be used to exclude any participant from any analysis set, nor to exclude any data from participants included in an analysis set.

The study non-compliance handling plan outlines the management of PDs and includes the proposed specific categories of PDs in this trial. Any PDs which are not defined as important will not be reported and discussed in the CSR.

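### Excluding the Japanese SMO-site participants from every analysis set would leave the adverse events of any who were dosed out of the planned safety output

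*SAP*

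**What the plan says.** SAP 2.1.4 (Handling of Other Issues Impacting Analysis Sets) describes an August 2023 inspection of an SMO in Japan that found significant GCP deviations at the sites it supported. The rule that follows covers "Any Japanese participants enrolled from sites managed by the SMO" and says that they "will be excluded from all analysis sets". Site identities are redacted and no count is visible.

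The sets defined in SAP 2.1 are Enrolled, Randomised, FAS (with its co-morbid subset), Safety, PK and Additional FU. Two matter most here:

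- **Randomised Analysis Set:** "This analysis set comprises all participants randomised to study treatment, irrespective of whether IP was subsequently taken". It is also assigned to the reporting of disposition.
- **Safety Set (SAP 2.1.2):** "This analysis set comprises all participants who received at least one dose of IP". The same section adds: "Safety analyses will be performed using all participants in the safety analysis set".

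Protocol 9.3 defines the Safety Set as "All participants who received at least one dose of IMP", with no exception for sites.

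**The concern.** GCP findings at a site can make its efficacy measurements unusable. They do not undo exposure. A participant who received study drug at one of these sites belongs to the exposed population as Protocol 9.3 defines it, however poor the records.

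Under the rule as written, such a participant leaves the only set on which safety is analysed, and nothing else in the SAP brings their events back. The AESIs in Protocol 8.3.6 include serious cardiac events, malignancy and serious infections, for which single events can matter. The report would also give no view of whether the co-primary estimates change when these participants are included.

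**Working it through.** **1. Does the exclusion reach safety?** SAP 2.1.4 names all analysis sets, SAP 2.1 counts the Safety Set among them, and SAP 2.1.2 bases safety analyses on that set. So it does, for anyone dosed.

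**2. Is there another route into the report?**

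| Place in the SAP | What it provides | Covers the SMO sites? |
|---|---|---|
| 2.1.2 | Separate safety listing for participants given a treatment other than the randomised one | No |
| 2.1.4, duplicate randomisations | Later participations listed and discussed in the CSR | No |
| 2.1.4, site with the May 2024 data-quality issue | Only the NPSD data excluded; details promised in the CSR | No; a different site |
| 2.1.4, general clause | Sensitivity analysis with a site removed, as an option | Not used here |
| 4.2.6.3 and 4.2.6.4 | Worst-score composite, COVID-19 hypothetical, rank ANCOVA, control-based imputation, tipping point | None adds these participants |
| 4.2.10.1 | AE tables; listing of events sent for adjudication | Under the Safety Set rule in 2.1.2, no |

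**3. Is the departure recorded?** SAP Section 1 says that changes from the protocol will be described. Section 6 lists only two added exploratory analyses. The SAP amendment history does log the addition of the GCP findings to 2.1.4, dated 21 August 2024.

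**4. Disposition.** The SAP's definitions assign disposition to the Enrolled and Randomised sets, but 4.2.1 uses an All participants analysis set that 2.1 does not define. Whether the SMO-site participants appear in the disposition table is therefore unsettled.

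**5. Size for safety (illustration).** The documents give neither the number dosed at these sites, k, nor an SAE risk. Assume k from 1 to 20 (0.25% to 5% of 400) and a 5% SAE risk each. The chance that at least one SAE is missing is 1 − 0.95^k, and the expected number missing is 0.05k.

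| k | Share of 400 | Expected SAEs missing | Chance of at least one |
|---|---|---|---|
| 1 | 0.25% | 0.05 | 5% |
| 5 | 1.25% | 0.25 | 23% |
| 10 | 2.5% | 0.5 | 40% |
| 20 | 5% | 1 | 64% |

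**6. Size for efficacy.** Protocol 9.2 states at least 95% total power with 200 per arm at the two-sided 1% level. Power for a difference d with standard deviation s is Φ(d / (s√(2/n)) − 2.576).

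- NPS: 1.8 / (2.25 × √(2/200)) = 1.8 / 0.225 = 8.00, and 8.00 − 2.576 = 5.42, so power is above 99.999%.
- NCS: 0.87 / (1.22 × √(2/200)) = 0.87 / 0.122 = 7.13, and 7.13 − 2.576 = 4.56, so power is 99.9997%.

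The product is 99.9997%, which is consistent with the stated figure. At 195, 190 and 180 per arm (10, 20 and 40 participants lost, split evenly) joint power stays above 99.99%.

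Time to surgery decision has far less margin. With a hazard ratio of 0.33 and a placebo rate of 11%, the tezepelumab rate is 1 − 0.89^0.33 = 3.77%. Expected events are 200 × (0.11 + 0.0377) = 29.5. Schoenfeld power at 5% is Φ(√29.5 × |ln 0.33| / 2 − 1.96) = 85.4%. It falls to 84.5%, 83.6% and 81.6% at 195, 190 and 180 per arm. A two-proportion calculation gives 79.1% at 200 and 74.8% at 180. Either way, losing 20 participants costs about two points.

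**The case against.** The strongest reply is that the SAP provides for exactly this. SAP 2.1.4 says its set definitions presuppose data integrity at every site and allows exclusion from analysis sets for serious non-compliance. SAP 2.1 allows removal from the reporting of the study. Protocol 9.4 leaves the description of analysis populations to the SAP and requires deviations to be reported in the CSR. The exclusion follows a regulator's inspection, is applied by site and not by arm, and appears openly in the SAP and its amendment history. All of this stands, and it settles the efficacy side. It does not supply the missing safety data: a permission to exclude is not a plan to show what was excluded.

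A reader might infer three stronger things that the documents do not support.

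- *That dosed participants are known to be lost.* The protocol uses enrolled to mean having signed consent, which includes screen failures. With the details redacted, the number dosed could be zero. The redaction is no fault of the plan.
- *That the rule contradicts SAP 2.2*, where "important PDs will not be used to exclude any participant from any analysis set". That sentence concerns important protocol deviations. Site-level non-compliance has its own, more specific rule in 2.1.4, so the two can be read together.
- *That serious events would go unseen.* Protocol 8.3.8 still requires SAEs to reach the sponsor within 24 hours, and Protocol 8.3.9 still sends cardiac events, deaths and malignancies to adjudication. The gap is in the CSR output.

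**Conclusion.** The point holds for safety reporting. Followed literally, the plan omits the adverse events of any SMO-site participant who was dosed from the CSR safety output, and so departs from Protocol 9.3. This rests on the text alone and needs no assumption about numbers.

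The size cannot be read from the documents. Under the assumed range it is zero to about one SAE and at most 5% of participants. The relative effect is larger within Japan, which is a stratification region (SAP 1.2), a subgroup (SAP 3.1.6) and a registration population (SAP 4.2.14).

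A reader might also infer that the co-primary result hangs on the exclusion. Nothing suggests that: the power margin is very wide and the exclusion is not tied to treatment arm. Analysing the co-primaries with these participants included is for transparency.

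**What to change.** In SAP 2.1.4:

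- Limit the exclusion to the FAS-based efficacy analyses and the PK analyses.
- Keep these participants in the Enrolled and Randomised sets, and name in 4.2.1 a defined set for the disposition table.
- State the number excluded by arm.
- For those dosed, list all AEs, SAEs, deaths, AESIs and discontinuations separately, outside the main safety tables.
- Add one sensitivity analysis of both co-primary endpoints that includes those randomised and dosed.
- Note the departure from Protocol 9.3 in SAP Section 6.

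SAP 2.1.4 bars SAP updates after primary database lock. If lock has passed, the same items belong in the CSR.

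The cost is a few sentences, one listing and one more run of the co-primary model. The downside is that records from non-compliant sites appear in a listing and one sensitivity analysis, where they can be labelled as such.
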